4. STUDY DESIGN

4.1 General Description

This is an observational, multicenter and cross-sectional study in NVAF elderly patients currently on NOAC treatment for their stroke prevention.

AF is classified as non-valvular AF in the absence of mitral stenosis or cardiac valvular prosthesis, since NOACs are not recommended for patients with mechanical heart valve (level of evidence B) or moderate to severe mitral stenosis (level of evidence C) (3).

The study will be conducted in approximately 50 sites in Spain. Investigators from different specialties are planned to be included as follows: 35 cardiologists, 10 hematologists and 5 geriatricians.

Document:	H:\HOR-Europe\2019\2512352 - Study on anticoagulation management - BI\Proyecto\Estadística\SAP\SAP_REBELD_version1.0_08072020.docx		
Author:		Version Number:	Version 1.0
		Version Date:	[08072020]

Template No.: RWI_TP_BIOS0013 Revision 1

Reference: RWI_WI_BIOS0015

Effective Date: 15Jun2018

The design of the study imposes a single visit to be performed for the informed consent signature and data collection that will coincide with one of those performed by the patients as part of routine follow-up of their disease, without interfering with usual clinical practice of the investigator.

A specific therapeutic strategy has already been assigned to each included patient, based on routine practice and without interference with the physician's prescription habits. The observational nature of the study is ensured as no diagnostic or therapeutic intervention outside of routine clinical practice will be applied.

Cardiology, hematology, geriatric services at a hospital setting, specialty medical offices and nursing homes, who regularly prescribe NOACs for stroke prevention in NVAF patients may be invited to participate.

The number of patients per site to be included in the study will be initially set up to a maximum of 10 patients per site. Once the 50% of the participating sites have been initiated, the recruitment will become competitive until the end of the study and the limitation of 10 patients per site will be removed to allow sites to continue with the recruitment.

4.2 Study size

It is planned that a total of approximately 500 patients will be recruited for the study. Based on such a sample size estimate, categorical variables of binomial proportions (e.g. sex) will be estimated with the precision (i.e. width of descriptive 95% confidence interval) described in the following Table 1. Calculations of the confidence intervals (CI) are based on the Clopper-Pearson method:

Document:	H:\HOR-Europe\2019\2512352 - Study on anticoagulation management - BI\Proyecto\Estadística\SAP\SAP_REBELD_version1.0_08072020.docx		
Author:	██████████	Version Number:	Version 1.0
		Version Date:	[08072020]

Template No.: RWI_TP_BIOS0013 Revision 1

Reference: RWI_WI_BIOS0015

Effective Date: 15Jun2018

**Table 1. Width of 95% confidence interval by prevalence**

Prevalence of attribute	Sample size
	500
10% Expected n	50
95% CI width	5.46%
20% Expected n	100
95% CI width	7.20%
30% Expected n	150
95% CI width	8.22%
40% Expected n	200
95% CI width	8.76%
50% Expected n	250
95% CI width	8.76%

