2. INTRODUCTION

This statistical analysis plan (SAP) describes the rules and conventions to be used in the presentation and analysis of treatment patterns and patient profile. It describes the data to be summarized and analyzed, including specifics of the statistical analyses to be performed.

This statistical analysis plan (SAP) is based on protocol version 1.0, dated 24 May 2019 and case report forms (CRFs) version 2, dated 10 March 2020.

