4.6 Changes to Analysis from Protocol

Per protocol, the variable “reason for VKA switch will be described under the OAC treatment management outcome. Finally, reason for VKA treatment switch has not been collected specifically in the VKA section of the CRF. This has been deleted from section 14.2.2 of SAP.

New analysis not included in the final protocol have been considered:

- Antiplatelet treatment according to current NOAC type
- Treatment received at the moment of thromboembolic and bleeding events.
- For all NOACs, the different doses that patients take according to HAS-BLED score.
- Underdosed and overdosed patients (for current NOAC treatment).
- HAS-BLED total score according to NOAC and antiplatelet current treatment.
- Multivariate model to evaluate the association between the Clinical Frailty Scale (dependent variable) and the thromboembolic and the bleeding events (independent variables). To calculate this analysis, only events that have occurred subsequent to the start of anticoagulant therapy (not those prior to the start of VKA / NOACs) will be considered. Univariate analysis will be performed. All variables which have a P value of less than 0.1 will be included in the multivariate analysis.

Document:	H:\HOR-Europe\2019\2512352 - Study on anticoagulation management - BI\Proyecto\Estadistica\SAP\S		
	AP_REBELD_version1.0_08072020.docx		
Author:	██████████	Version Number:	Version 1.0
		Version Date:	[08072020]

Template No.: RWI_TP_BIOS0013 Revision 1

Reference: RWI_WI_BIOS0015

Effective Date: 15Jun2018

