17.3 Outcomes

17.3.1 Primary outcome: Current NOAC

Table 27. Type of NOAC, dose and duration since first NOAC initiation at study visit according to sex

		Male	Female	Total
Current NOAC	Valid N Dabigatran Rivaroxaban Apixaban Edoxaban N missing			
Dabigatran dose	Valid N 110mg BID 150mg BID N missing			
Rivaroxaban dose	Valid N 15mg QD 20mg QD N missing			
Apixaban dose	Valid N 2.5mg BID 5mg BID N missing			
Edoxaban dose	Valid N 30mg QD 60mg QD N missing			

Document: H:\HOR-Europe\2019\2512352 - Study on anticoagulation management - BI\Proyecto\Estadística\SAP\S AP_REBELD_version1.0_08072020.docx

Author: Version Number: Version 1.0
Version Date: [08072020]

Template No.: RWI_TP_BIOS0013 Revision 1

Reference: RWI_WI_BIOS0015

Effective Date: 15Jun2018

		Male	Female	Total
Years since first NOAC initiation to study visit	Valid N Mean (SD) Median (Q1-Q3) Min-Max N missing			

BDI: twice a day; QD: once a day

Table 28. Type of NOAC, dose and duration since fist NOAC initiation at study visit according to age

		75-79 years	80-84 years	≥85 years	Total
Current NOAC	Valid N Dabigatran Rivaroxaban Apixaban Edoxaban N missing				
Dabigatran dose	Valid N 110mg BID 150mg BID N missing				
Rivaroxaban dose	Valid N 15mg QD 20mg QD N missing				
Apixaban dose	Valid N 2.5mg BID 5mg BID N missing				
Edoxaban dose	Valid N 30mg QD 60mg QD N missing				
Years since first NOAC initiation to study visit	Valid N Mean (SD) Median (Q1-Q3) Min-Max				

Document: H:\HOR-Europe\2019\2512352 - Study on anticoagulation management - BI\Proyecto\Estadística\SAP\S
AP_REBELD_version1.0_08072020.docx

Author: [REDACTED] Version Number: Version 1.0
Version Date: [08072020]

Template No.: RWI_TP_BIOS0013 Revision 1

Reference: RWI_WI_BIOS0015

Effective Date: 15Jun2018

		75-79 years	80-84 years	≥85 years	Total
	N missing				

BDI: twice a day; QD: once a day

Table 29. Type of NOAC, dose and duration since fist NOAC initiation at study visit according to heart failure

		Heart failure		
		No	Yes	Total
Current NOAC	Valid N Dabigatran Rivaroxaban Apixaban Edoxaban N missing			
Dabigatran dose	Valid N 110mg BID 150mg BID N missing			
Rivaroxaban dose	Valid N 15mg QD 20mg QD N missing			
Apixaban dose	Valid N 2.5mg BID 5mg BID N missing			
Edoxaban dose	Valid N 30mg QD 60mg QD N missing			
Years since first NOAC initiation to study visit	Valid N Mean (SD) Median (Q1-Q3) Min-Max N missing			

BDI: twice a day; QD: once a day

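### SAP Table 1 gives a 95% CI width of 8.76% at 50% prevalence; the stated Clopper-Pearson method gives 8.94%, as the protocol prints

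*SAP*

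**What the plan says.** SAP section 4.2 sets the size of the study: "It is planned that a total of approximately 500 patients will be recruited for the study". It expresses precision as the full "width of descriptive 95% confidence interval" for a binomial proportion and names the method: "Calculations of the confidence intervals (CI) are based on the Clopper-Pearson method". The table that follows, "Table 1. Width of 95% confidence interval by prevalence", has five rows for n = 500. The printed widths at 10, 20, 30, 40 and 50% prevalence are 5.46, 7.20, 8.22, 8.76 and 8.76%.

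Protocol section 9.5 has the same sample size, the same precision measure and the same method. Its Table 4 prints 5.46, 7.20, 8.22, 8.76 and 8.94%. The two tables differ only in the 50% row.

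The SAP's introduction ties it to that protocol: "This statistical analysis plan (SAP) is based on protocol version 1.0, dated 24 May 2019". SAP section 4.6, on changes from the protocol, does not mention the precision table.

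**The concern.** Two rows of one table, with the same sample size and method but different prevalences, show the same width. A binomial interval at fixed n is widest at 50%, so the 40% and 50% cells should differ visibly at two decimals.

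The 50% row is the worst case and therefore the figure a reader would quote as the study's guaranteed precision for a whole-sample proportion. As printed, the SAP makes 500 patients look slightly more informative than they are, and it disagrees with the protocol it says it follows. A report author who copies the SAP table would carry the wrong value forward.

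**Working it through.** **Inputs.** n = 500, two-sided 95% confidence, full interval width and Clopper-Pearson limits, all from SAP section 4.2 and identical in protocol section 9.5. Expected counts x = 50, 100, 150, 200 and 250, from the tables.

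**Formula.** Lower limit = 2.5% quantile of Beta(x, n − x + 1). Upper limit = 97.5% quantile of Beta(x + 1, n − x). Width = upper − lower.

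**Results (percent).**

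| Prevalence | Limits | Exact width | Difference of limits rounded to two decimals | Protocol Table 4 | SAP Table 1 |
|---|---|---|---|---|---|
| 10% | 7.51 to 12.97 | 5.457 | 5.46 | 5.46 | 5.46 |
| 20% | 16.58 to 23.78 | 7.199 | 7.20 | 7.20 | 7.20 |
| 30% | 26.01 to 34.23 | 8.215 | 8.22 | 8.22 | 8.22 |
| 40% | 35.68 to 44.44 | 8.767 | 8.76 | 8.76 | 8.76 |
| 50% | 45.53 to 54.47 | 8.943 | 8.94 | 8.94 | **8.76** |

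Subtracting the rounded limits reproduces all five protocol cells and the first four SAP cells. It also explains why the 40% cell reads 8.76 although the exact width is 8.767. The SAP's 50% cell is the only one that fails.

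**Could it be rounding?** No. The gap is 8.94 − 8.76 = 0.18 percentage points, and the rounding rule that fits the other nine cells gives 8.94.

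**Could it be another method?** The normal approximation at 50% gives 2 × 1.96 × √(0.5 × 0.5 / 500) = 8.765%, which is close to the printed figure. In the other four rows, however, it gives 5.26, 7.01, 8.03 and 8.59%, where the SAP prints 5.46, 7.20, 8.22 and 8.76%. Other common intervals at 50% do not give 8.76 either: Wilson 8.732, Agresti-Coull 8.732, Jeffreys 8.744, and the normal approximation with continuity correction 8.965. No single method yields the SAP's five rows.

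**Size.** 0.18 / 8.94 = 2.0% of the width. As a scale only, a Clopper-Pearson width of about 8.76% at 50% prevalence corresponds to roughly 520 patients (8.766% at n = 520).

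**The case against.** The printed cell itself cannot be defended; the fair objections concern its weight.

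- **It is a slip without consequence.** The planned number is only approximate, the table is descriptive, and no target width is set anywhere. The figure of about 520 patients therefore does not mean the study is 20 patients short. The SAP (version 1.0, file date 08072020) also postdates the planned end of data collection on 27 April 2020 in protocol section 6, so on that timetable the table could not have steered recruitment. All of this stands, and it limits the point to a minor correction.
- **The silence of SAP section 4.6 proves little.** That section lists changes to analyses, for example "New analysis not included in the final protocol have been considered", and a miscopied precision table would not be expected there. This also stands. The silence shows only that no deliberate change is declared.
- **The cause is unknown.** The value could be a repeat of the 40% row or a normal-approximation figure placed in one cell. The documents do not settle which, but the correction is the same either way.

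Damage from reading the PDF is not a plausible explanation: the SAP table is complete, and its other four rows match the protocol exactly.

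**Conclusion.** The concern holds. Under the method, confidence level and sample size that the SAP states, the width at 50% prevalence is 8.94%, not 8.76%. The SAP understates its worst-case interval width by 0.18 percentage points and contradicts protocol Table 4.

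The result needs no assumption beyond the SAP's own inputs: n taken as exactly 500, as in the table, and patients treated as independent, as the Clopper-Pearson method requires. The error is certain but minor. The sample size, the planned analyses and the interpretation of the study do not depend on it.

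**What to change.** In SAP Table 1, change the width in the 50% row from 8.76% to 8.94%, so that it agrees with protocol Table 4. The other four rows and the protocol need no change. The cost is one table cell, with no additional patients, data or analyses.

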4.3 Description of treatment

Patients in this study will be currently on treatment with NOAC for their NVAf, according to the indication approved in their SmPC, and initiated it at least 3 months before the study visit. Prescription of the treatments will have been done under the sole responsibility of the healthcare professional and before considering the participation in the study.

In addition, no intervention, either diagnostic or therapeutic, will be applied to patients other than that used for routine clinical practice.

Document: H:\HOR-Europe\2019\2512352 - Study on anticoagulation management - BI\Proyecto\Estadística\SAP\S
AP_REBELD_version1.0_08072020.docx

Author: [REDACTED] Version Number: Version 1.0
Version Date: [08072020]

Template No.: RWI_TP_BIOS0013 Revision 1

[figure not shown]
Reference: RWI_WI_BIOS0015

Effective Date: 15Jun2018

4.4 Study flow/schedule

The design of the study imposes a single visit to be performed for the informed consent signature and data collection that will coincide with one of those performed by the patients as part of routine follow-up of their disease, without interfering with usual clinical practice of the investigator.

Figure 1. Study scheme for study period

After signing the informed consent, investigator will assess the Clinical Frailty Scale (1), the Modified EHRA scale for AF related symptoms (4), the NYHA classification of heart failure (5) and the CHA2DS2-VASc and HAS-BLED scales and include the scores directly in eCRF after evaluating the patient's functional status and patient's medical records. The investigator will review the medical records in order to complete other variables needed to address study objectives that will mainly be obtained directly from patient medical records or requested to the patient at the study visit if not available in medical records. The end of the single study visit is the end of the study for each patient.

Document:	H:\HOR-Europe\2019\2512352 - Study on anticoagulation management - BI\Proyecto\Estadística\SAP\S		
	AP_REBELD_version1.0_08072020.docx		
Author:	██████████	Version Number:	Version 1.0
		Version Date:	[08072020]

Template No.: RWI_TP_BIOS0013 Revision 1

Reference: RWI_WI_BIOS0015

Effective Date: 15Jun2018

4.5 Schedule of Events

The schedule of events can be found in Section 6 of the protocol (Milestones).

4.6 Changes to Analysis from Protocol

Per protocol, the variable “reason for VKA switch will be described under the OAC treatment management outcome. Finally, reason for VKA treatment switch has not been collected specifically in the VKA section of the CRF. This has been deleted from section 14.2.2 of SAP.

New analysis not included in the final protocol have been considered:

- Antiplatelet treatment according to current NOAC type
- Treatment received at the moment of thromboembolic and bleeding events.
- For all NOACs, the different doses that patients take according to HAS-BLED score.
- Underdosed and overdosed patients (for current NOAC treatment).
- HAS-BLED total score according to NOAC and antiplatelet current treatment.
- Multivariate model to evaluate the association between the Clinical Frailty Scale (dependent variable) and the thromboembolic and the bleeding events (independent variables). To calculate this analysis, only events that have occurred subsequent to the start of anticoagulant therapy (not those prior to the start of VKA / NOACs) will be considered. Univariate analysis will be performed. All variables which have a P value of less than 0.1 will be included in the multivariate analysis.

Document:	H:\HOR-Europe\2019\2512352 - Study on anticoagulation management - BI\Proyecto\Estadistica\SAP\S		
	AP_REBELD_version1.0_08072020.docx		
Author:	██████████	Version Number:	Version 1.0
		Version Date:	[08072020]

Template No.: RWI_TP_BIOS0013 Revision 1

Reference: RWI_WI_BIOS0015

Effective Date: 15Jun2018

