7. GENERAL CONSIDERATIONS

The design of the study imposes a single visit to be performed and that will coincide with one of those performed by the patients as part of routine follow-up of their disease, without interfering with usual clinical practice of the investigator.

Data will be collected through an eCRF which will include all the study variables.

Investigator will enter patient data in eCRF. Variables collected at the time of the study visit (including those related to the first NOAC initiation) will be obtained based on and limited to those available in the medical records of the selected patients. Demographic characteristics, smoking habit and alcohol consumption may be asked to the patient at the study visit if not available in the medical records. LVEF measurement will be obtained from the last images available for the patient.

Document:	H:\HOR-Europe\2019\2512352 - Study on anticoagulation management - BI\Proyecto\Estadistica\SAP\SAP_REBELD_version1.0_08072020.docx		
Author:		Version Number:	Version 1.0
		Version Date:	[08072020]

Template No.: RWI_TP_BIOS0013 Revision 1

Reference: RWI_WI_BIOS0015

Effective Date: 15Jun2018

Clinical Frailty Scale, modified EHRA scale for AF related symptoms, NYHA classification for heart failure, CHA2DS2-VASc and HAS-BLED scores will be assessed by the investigators at the study visit by evaluating the patient's functional status and medical records and the values will be directly included in the eCRF.

Final score for the Comorbidities Charlson Index will be automatically calculated based on the answers individually entered by the investigator in the eCRF for each index item (6).

Any required missing data to calculate the score for the scales or the Comorbidities Charlson Index may be asked to the patient at the study visit if not available in the medical records and should be documented, however the final score number obtained by the investigator from this information will not need to be included in medical records.

Boehringer Ingelheim reserves the right to discontinue the study overall or at a particular study site at any time for the following reasons:

1. Failure to meet expected enrolment goals overall or at a particular study site
2. Administrative reasons (i.e. study rejected by the hospital director)
3. Violation of GxP (as applicable), the study protocol, or the contract by a study site or investigator, disturbing the appropriate conduct of the study

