Comorbidities and Clinical Risk Factors: - Heart Failure (Yes/No, New York Heart Association (NYHA) classification; Left Ventricular Ejection Fraction, LVEF, %) - Coronary artery disease (Yes/No) - Sleep apnoea-hypopnoea syndrome (SAHS) (Yes/No) - Hypertension (Yes/No) -Hyperlipidemia (Yes/No) - Comorbidity Charlson index (Yes/No; total score): myocardial infarction (already collected for history of thromboembolic events), congestive heart failure (already collected for the NYHA scale scoring), cerebral and peripheral vascular disease, dementia, chronic obstructive pulmonary disease, connective tissue disease, peptic ulcer disease, mild/moderate/severe liver disease, diabetes, diabetes with end-organ damage, hemiplegia, moderate/severe renal disease, any solid tumor, metastatic solid tumor, leukemia, lymphoma AIDs, age (already collected as a demographic characteristic). -History of thromboembolic events (Yes/No, number and date): TIA, ischemic stroke, hemorrhagic stroke, embolism systemic, deep vein thrombosis, pulmonary embolism, stable angina, unstable angina, myocardial infarction with/without ST segment elevation; and bleeding events (Yes/No, number and date): intracranial, digestive, genitourinary, gingival, nasal, pulmonary, articular-muscular, conjunctival.	x	x (NYHA classification, Charlson Index)
CHA2DS2-VASc (total score)		x
HAS-BLED (total score)		x
Clinical Frailty Scale		x
Previous vitamin K antagonist (VKA) treatment (yes/no), type (acenocoumarol or warfarin), start date and treatment duration		
Other concomitant treatments (Total number of current concomitant drugs; Type (Yes/No, number): ARB or ACE inhibitor, Beta-blocker, Calcium channel blockers, Diuretics, Amiodarone, Statin, Proton pump inhibitor, H2-receptor antagonist, Digoxin, NSAIDs, Dronedarone, Other antiarrhythmics, ketoconazole (systemic), cyclosporine, itraconazole	x	

Document: H:\HOR-Europe\2019\2512352 - Study on anticoagulation management - BI\Proyecto\Estadística\SAP\S AP_REBELD_version1.0_08072020.docx

Author: [REDACTED] Version Number: Version 1.0
Version Date: [08072020]

Template No.: RWI_TP_BIOS0013 Revision 1

Reference: RWI_WI_BIOS0015

Effective Date: 15Jun2018

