14.6 Exploratory analysis

History and current antiplatelet treatment will be described by current NOAC type.

Treatment received at the time of thromboembolic and bleeding events will be described, including NOAC, VKA and antiplatelet treatments.

Doses of current NOAC treatment received by the patient will be described according to HAS-BLED score (as low, intermediate and high risk).

The percentage of underdosed and overdosed patients for current NOAC treatment will be described.

HAS-BLED total score (as <3 , $3-5$, ≥ 5) will be described according to NOAC and antiplatelet current treatment.

Multivariate logistic regression will be used to evaluate the association between the Clinical Frailty Scale (dependent variable: Frailty patients - CFS scoring >4 vs Non-frailty patients - CFS scoring ≤ 4) and the thromboembolic and the bleeding events (independent variables). To calculate this analysis, only events that have occurred subsequent to the start of anticoagulant therapy (not those prior to the start of VKA / NOACs) will be considered. Other factors will be age, sex, BMI, smoking habit, alcohol consumption, time since NVAf diagnosis, NVAf type, modified EHRA scale, procedures and interventions, comorbidity Charlson index and clinical risk factors. Univariate analysis will be performed. All variables which have a P value of less than 0.1 will be included in the multivariate analysis.

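### The exploratory frailty regression can adjust the event terms for variables recorded after the events or built from them, and the plan reports no adjusted model without these variables

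*SAP*

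**What the plan says.** The model is not in the protocol; SAP 4.6 lists it among the new analyses, as a "Multivariate model to evaluate the association between the Clinical Frailty Scale (dependent variable) and the thromboembolic and the bleeding events (independent variables"). SAP 14.6 gives the detail: "Multivariate logistic regression will be used to evaluate the association between the Clinical Frailty Scale", split at CFS >4 versus ≤4, and the thromboembolic and bleeding events. Only events after the start of VKA or NOAC count. The other factors are age, sex, BMI, smoking, alcohol, time since NVAF diagnosis, "NVAf type, modified EHRA scale, procedures and interventions, comorbidity Charlson index and clinical risk factors". The selection rule is "All variables which have a P value of less than 0.1 will be included in the multivariate analysis". The Table 53 footnote repeats the list and the rule.

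Four other places fix what these covariates are and when they are recorded:

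- **Visit ratings.** SAP 4.4 says that, after consent, the "investigator will assess the Clinical Frailty Scale (1), the Modified EHRA scale for AF related symptoms (4), the NYHA classification of heart failure (5") and other scores. SAP 7 repeats this for the single study visit.
- **Clinical risk factors.** Mock Table 11, which has this title, contains NYHA class and LVEF.
- **Procedures.** SAP Table 3 records PCI/CABG as yes/no and lists no date. The same table counts "stable angina, unstable angina, myocardial infarction with/without ST segment elevation" as thromboembolic events, with number and date.
- **Charlson index.** SAP Table 2 gives one point for myocardial infarction and one for cerebrovascular accident or TIA. SAP Table 3 notes that the infarction item comes from the thromboembolic event history.

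**The concern.** With a single visit, every counted event happened before the CFS was rated. The modified EHRA class and NYHA class used as adjusters are also rated at that visit, so they too come after the events. A PCI or CABG may have been done because of the angina or infarction that counts as the exposure. The Charlson index contains some of the exposure events as items.

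Conditioning on a variable that the event has changed removes the part of the association that runs through it. Conditioning on an index that scores the event makes the event compete with itself. The event odds ratios in Table 53 would then describe whether patients with events are frailer at the same current symptom class, procedure history and comorbidity score. A weak event term could be read as no link between events and frailty when the adjustment produced it. This is the only regression in the SAP, and Table 53 shows only the multivariate fit.

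**Working it through.** **The plan's own figure.** The documents give no power or precision for this model. Their only design calculation is the 95% Clopper-Pearson width at n=500. Recomputed for prevalences of 10, 20, 30, 40 and 50%, the widths are 5.46, 7.20, 8.21, 8.77 and 8.94%. This matches protocol Table 4 to rounding. The present point does not depend on it.

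**Position of each covariate relative to the events**

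| Covariate | Recorded | Relation to events and outcome |
|---|---|---|
| Modified EHRA | At the visit, with CFS | After all events. Runs from none to disabling symptoms, while CFS grade 4 (protocol Annex 3) is described by symptoms limiting activity. Clearest overlap. |
| NYHA | At the visit, with CFS | After all events. Tabulated as objective-evidence grades A-D, so less overlap with function. |
| PCI/CABG | Yes/no, no date listed | May follow or precede an event. Relevant to angina and infarction only. |
| Charlson | Computed from items | Scores infarction and CVA/TIA, which are exposure events. |
| LVEF | Last available images (SAP 7) | Timing open; not rated at the visit. |

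**Size under assumed inputs.** The documents give no event rate, frailty rate or effect size. The following are therefore assumptions: 15% with an event; 30% in the high symptom class without an event; direct event odds ratio 1.5; 20-32% frail.

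- Mediator layout: logit P(high class) = ln(0.3/0.7) + g × event.
- Frailty: logit P(frail) = -1.4 + ln(1.5) × event + b × class.
- Confounder layout: the class comes first (35% high) and raises the event odds by exp(g).
- Share removed = 1 - ln(OR with class) / ln(OR without class).

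With one million simulated patients per row:

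| Layout | exp(g) | exp(b) | OR without class | OR with class | Log OR removed |
|---|---|---|---|---|---|
| Mediator | 1 | 4 | 1.44 | 1.50 | -11% |
| Mediator | 2 | 2 | 1.67 | 1.51 | 20% |
| Mediator | 4 | 2 | 1.88 | 1.51 | 35% |
| Mediator | 4 | 4 | 2.26 | 1.50 | 50% |
| Confounder | 2 | 2 | 1.66 | 1.49 | 21% |
| Confounder | 4 | 4 | 2.25 | 1.50 | 50% |

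For example, ln 1.67 = 0.513 and ln 1.51 = 0.412, and 1 - 0.412/0.513 = 0.20. In the first row the event does not change the class. Nothing is removed, and the small rise is non-collapsibility of the odds ratio.

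**With the P<0.1 screen** (n=500, 600 runs, mediator layout, direct odds ratio 1.5):

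| exp(g), exp(b) | Class enters | Event term passes | Mean OR without class | Mean OR after screen |
|---|---|---|---|---|
| 2, 2 | 96% | 64% | 1.69 | 1.52 |
| 2, 4 | 100% | 73% | 1.77 | 1.47 |
| 4, 4 | 100% | 93% | 2.27 | 1.50 |
| 4, 1.2 | 31% | 50% | 1.59 | 1.52 |

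A class tied to frailty nearly always enters. The event term, which is the purpose of the model, fails its own screen in 7-50% of runs.

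**A second layout** treats CFS and the symptom scale as two noisy ratings of one underlying function that the event shifts (n=500, 20% with events, 35% frail). For correlations of 0.3 to 0.7 it removes 22-49% of the log odds ratio. If the event shifts only the CFS, the odds ratio rises instead, from 2.19 to 2.52 in one such run.

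**The case against.** The strongest objection is that attenuation is assumed, not shown. The confounder rows above fall as far as the mediator rows, and there the fall is correct adjustment. Earlier heart failure, symptoms or revascularisation could raise both event risk and frailty. The SAP speaks only of an association, so an association conditional on current symptoms is a legitimate exploratory quantity. Entry depends on P<0.1, and a univariate analysis is planned, so the crude association will at least be computed. The analysis is exploratory, in a study described as descriptive.

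Most of this stands, and it limits the point in four ways:

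- A reader might infer that the model is necessarily biased towards no association and loses power. The documents do not support that. It holds only if events worsen the classes or lead to the procedures.
- A reader might infer that NYHA duplicates the CFS as a function rating. Table 11 grades it by objective evidence of disease, so the overlap case rests mainly on modified EHRA.
- A reader might want LVEF removed as a visit rating. SAP 7 takes it from the last available images, so that argument fails.
- The procedure argument reaches coronary events only, not bleeding, stroke or venous events.

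The objection does not remove the timing problem. The classes in the model are those rated at the visit, after every counted event, so they are at best proxies for the earlier state. Nor does it answer the Charlson overlap, which follows from the SAP's own scoring table. The univariate result has no place in Table 53 and is not adjusted even for age and sex.

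**Conclusion.** The point holds as a weakness of specification in an exploratory model. SAP 14.6 lets post-event and event-derived variables enter as adjusters, does not say whether a total or a conditional association is wanted, and plans no adjusted model without them. The event odds ratios in Table 53 are attenuated if events worsen these classes or lead to these procedures, and properly adjusted if the classes or procedures came first. The data cannot separate the two.

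The documents therefore give no size. The 20-50% loss of the log odds ratio rests on the assumed rates and on a mediator structure with links of odds ratio 2 to 4 each way. With no effect of events on the class, nothing is lost. None of this touches the primary or secondary objectives. It is worth correcting because the remedy is cheap and both results can be shown.

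**What to change.** In SAP 14.6 and the Table 53 footnote:

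1. Pre-specify a model in which the thromboembolic and bleeding event terms stay in regardless of the P<0.1 screen.
2. Adjust it for age, sex and other factors that the events cannot affect. Leave out modified EHRA, NYHA class, coronary interventions, and the Charlson items for infarction and CVA/TIA. The Charlson answers are entered item by item, so the reduced score can be recomputed.
3. Report the fuller model alongside it, and describe its event odds ratios as associations conditional on current symptoms and procedures.

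The cost is SAP wording, a second panel in Table 53 and one extra model run on data already collected. The downside is that the reduced model does not adjust for earlier heart-failure severity as graded by NYHA. That is the reason to show both models and not to replace one with the other.
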